## 8. STATISTICAL CONSIDERATIONS

This section describes the planned statistical analyses for this study.

### 8.1 Sample Size Considerations

The purpose of this study is to get feedback on the usability of the device prior to clinical trials. The sample size is based on similar usability studies.

### 8.2 Data Analysis

This document contains information that is the confidential and proprietary property of Bleep or its affiliates. Neither this document nor the information therein may be reproduced, used, or disclosed to or for the benefit of any third party without the prior consent of Bleep.

Several metrics will be recorded as part of the usability assessment. Dependent variables will include time to complete each setup, number of technical issues that occurred during the trial, and number of times subjects needed additional instructions. Independent variables will include the subject ID and CPAP interface device. The average time to complete each trial and number of technical issues will be computed and an analysis of variance (ANOVA) completed on the data set. In general, we expect to see average trial completion times significantly less for the DreamPort-Eclipse compared to the traditional mask, and overall an average time per subject of less than 5 minutes to setup the DreamPort-Eclipse.

Additionally, we expect no more than 1 technical setup error per subject using the DreamPort-Eclipse. Subjects will also complete a usability survey to evaluate their experience. We expect average Likert scores from subjects to be greater than 3 on the System Usability Scale (SUS) (Brooke 1996). The SUS is validated (Bangor, Kortum et al. 2008), ranks scores in 1-5 responses from “Strongly Disagree” to “Strongly Agree” and integrates Usable (8 items) and Learnable (2 items) (Lewis and Sauro 2009). Additionally, we will also use a custom survey to provide targeted feedback about our specific platform features. This will include ten questions presented using a 1 to 5 Likert scale. Questions will target overall enthusiasm, if they understood how to setup the interface, comfort of wear, effectiveness of training guides, and stumbling blocks. We expect average Likert scores >3.

Finally, as part of the user feedback from this task we may further update the device input specifications and use cases. The freeform survey feedback and discussions with sleep clinicians after the usability study will inform and design modifications for continued development in this program.

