Primary Endpoint:	
Primary Effectiveness Endpoint:
 
Several metrics will be recorded as part of the usability assessment. Dependent variables will include time to complete each setup, number of technical issues that occurred during the trial, and number of times subjects needed additional instructions. Subjects will also complete a survey at the end of the protocol to evaluate their experience with the different options.

Secondary Endpoints:	NA
Sample Size Estimation:	The purpose of this study is to get feedback on the usability of the device prior to clinical trials. The sample size is based on similar usability studies.
Data Collection:	
All data will be acquired from the research procedures performed during usability assessments on human individuals. Data that will be collected from subjects includes demographic data and survey feedback. All subjects will be represented by subject IDs in the data in order to de-identify data. The individuals that will have the ability to access the subject IDs includes only the principal investigator and sleep center sites.
 
The study will be conducted in accordance with applicable local regulations and national privacy laws. The clinical study will not commence at an investigational site until favorable opinion(s) from the respective Ethics Committee (EC)/ Institutional Review Board (IRB) has been received.

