## **4. STUDY ENDPOINTS**

### **4.1 Primary Effectiveness:**

The primary endpoints for this study will include time to complete each setup, number of technical issues that occurred during the trial, and number of times subjects needed additional instructions. Subjects will also complete a survey at the end of the protocol to evaluate their experience with the different options.

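### Does section 8.2 leave the count of extra instructions, one of three primary endpoints, without an analysis?

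*Combined protocol and SAP*

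**What the plan says.** Section 4.1 lists setup time first among the primary endpoints, followed by "number of technical issues that occurred during the trial, and number of times subjects needed additional instructions". The Protocol Summary, under Primary Effectiveness Endpoint, gives the same three: "time to complete each setup, number of technical issues that occurred during the trial, and number of times subjects needed additional instructions". Section 8.2 repeats that list as its dependent variables and then names subject ID and interface device as the independent variables. The next sentence reads "The average time to complete each trial and number of technical issues will be computed and an analysis of variance (ANOVA) completed"; the ANOVA is to be run on the data set.

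Section 8.2 then states five expectations:

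- Time against the mask: "we expect to see average trial completion times significantly less for the DreamPort-Eclipse compared to the traditional mask".
- Time in absolute terms: "overall an average time per subject of less than 5 minutes to setup the DreamPort-Eclipse".
- Errors: "we expect no more than 1 technical setup error per subject using the DreamPort-Eclipse".
- The standard usability scale: "We expect average Likert scores from subjects to be greater than 3 on the System Usability Scale".
- The custom ten-question survey: "We expect average Likert scores >3".

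Section 8.1 gives the purpose as obtaining usability feedback ahead of clinical trials, and bases the sample size on similar studies. It states no significance level, power or effect size.

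**The concern.** The sentence on computed results names two of the three primary measures, and no expectation mentions the third. Read narrowly, the instruction count is recorded and never reported, and two analysts could produce different sets of primary results, one with two endpoints and one with three.

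The count also carries information that the other results do not. Section 4.1 lists it separately from technical issues, and nothing says that a coached setup also counts as an issue. A subject talked through every DreamPort-Eclipse setup could still finish in under 5 minutes with no more than one error. The survey items on understanding the setup and on the training guides are opinion ratings and do not record how often help was given. If the count were lost, the study would lose its direct observation of whether users manage on the materials supplied.

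The wording on errors is a related worry: section 8.2 computes technical issues but frames its expectation in terms of setup errors.

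**Working it through.** The plan gives no figure to reproduce here, so the check is mainly a comparison of sections.

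**Step 1. Coverage of each primary endpoint.**

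| Endpoint (4.1) | Dependent variable in 8.2 | Named in the results sentence | Expectations in 8.2 |
|---|---|---|---|
| Setup time | yes | yes | 2 |
| Technical issues | yes | yes | 1 |
| Instructions needed | yes | no | 0 |

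The other two expectations concern the surveys: 2 + 1 + 0 + 2 = 5. The observation is correct: one of three endpoints has no named summary, and none of the five expectations refers to it.

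**Step 2. The sentences in order.** Section 8.2 gives three dependent variables, then two independent variables, then an ANOVA on the data set. Dependent and independent variables are the parts of an ANOVA model. Listing a variable as dependent and then fitting the model to the data set would ordinarily include that variable. Nothing excludes it, and nothing confines the ANOVA to two outcomes.

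**Step 3. What the expectations are.** They are worded as things the team expects to see. No section calls them success criteria, ties a decision to them, or undertakes to give one per endpoint. Technical issues on the traditional mask have no expectation either, and that is not a defect.

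**Step 4. The 0-to-90 range.** Section 3 gives 30 subjects and three setups per device, so 30 x 3 = 90 DreamPort-Eclipse setups. All five expectations are compatible with 0 to 90 of these needing help. This is a logical bound that applies to any outcome without a threshold. It shows no wrong result and gives no likely size.

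**Step 5. Whether either reading causes trouble.** Assume each test is made at 5% and the tests are independent (the plan states no level). The chance of at least one false positive is then:

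- two endpoints: 1 - 0.95^2 = 9.75%
- three endpoints: 1 - 0.95^3 = 14.26%

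The gap is 4.5 percentage points, and it disappears if the count is only described. Description is workable with 30 subjects. If 0 of 30 need help on a device, the exact 95% upper limit is 1 - 0.025^(1/30) = 11.6%; if 3 of 30 do, the exact interval is 2.1% to 26.5%. A paired test is also possible: a two-sided exact sign test gives 2 x 0.5^6 = 0.031 at 6 subjects against 0, and 2 x 0.5^5 = 0.063 at 5 against 0. These figures show that the count can be analysed on either reading. They do not measure harm from the present text.

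**Step 6. The two error terms.** Take a subject with one user error and one device fault. The score is 1 (within the expectation) if only user errors count as setup errors, and 2 (outside it) if every technical issue counts. Neither term is defined, so the example assumes that a device fault is not a setup error. The documents do not settle which meaning was intended, and imposing the broader one would tighten the sponsor's own expectation.

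**The case for a change.** The strongest case for a change is that this is a primary endpoint, the data are to be collected anyway, and one sentence would remove the doubt. A reader who takes the results sentence literally has grounds for reporting only two measures. The surveys cannot stand in for an observed count.

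Much of that stands. The results sentence is incomplete, the text does not say whether the count is tested or descriptive, and a single term for errors would be tidier. It does not show a rule or number in the plan that gives a wrong answer. The stated route to design changes is freeform feedback and discussion with sleep clinicians, so no decision in section 8.2 depends on a test of the count.

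Related questions do not add weight. The plan does not say whether the clock runs during help, whether sponsor support under section 9 could reach a timed setup, or what format the mask instructions take. Section 9 is headed as dealing with mechanical failures and does not say that sponsor staff coach subjects. Nothing in the documents shows that help or training differs by device. The case report forms and training materials, where such procedures may be set, are not among the documents.

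**Conclusion.** No change to the plan is needed. The gap is real but small: one of three primary endpoints is missing from one sentence, in a section that has already listed it as a dependent variable of the analysis that sentence describes. A competent analyst would report the count by device beside time and technical issues and say whether it was tested or described. Either course is feasible with 30 subjects.

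The conclusion rests on two assumptions: that a listed dependent variable is meant to be analysed, and that the expectations are forecasts and not pass/fail criteria. The text supports both. If the sponsor intended the five expectations as formal success criteria, the absence of one for the instruction count would deserve a second look, but no section says so. The difference between the two error terms is a looseness of wording that can be resolved when results are tabulated, by stating which events were counted.

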## **3. STUDY DESIGN**

This multicenter study will involve recruiting 30 adult subjects who are impacted by obstructive sleep apnea and currently are familiar with a CPAP device. Clinicians will screen subjects for cognitive deficits and serious mental health or medical conditions that would compromise subject safety or accurate user feedback. Prior to data collection and study enrollment, the protocol will be explained in detail to the subjects and informed consent will be obtained.

Participants will receive and review the training materials developed in Aim 1, including written and video instructions on how to use the DreamPort-Eclipse. They will also be provided with and review instructions on the traditional nasal mask used in this study. Participants will be requested to put on each of the different CPAP interface options a total of three times for a total of six trials. The order of device trials will be randomized.

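### The survey has only an absolute expectation (average Likert above 3), the SUS sentence names no interface, and no survey comparison with the mask is planned

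*Combined protocol and SAP*

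**What the plan says.** The Protocol Summary and section 1.1 set a comparative objective: usability of the new interface relative to a traditional nasal mask. Section 3 has 30 subjects, each of whom will "put on each of the different CPAP interface options a total of three times for a total of six trials", with the order of device trials randomised.

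The survey is described in the same sentence in the Protocol Summary, section 2 and section 4.1: "Subjects will also complete a survey at the end of the protocol to evaluate their experience with the different options". In section 4.1 that sentence follows the list of primary endpoints and is not part of the list.

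Section 8.2 is the only place that says how survey scores will be judged. For the SUS it says "We expect average Likert scores from subjects to be greater than 3 on the System Usability Scale (SUS". For the second instrument, "we will also use a custom survey to provide targeted feedback about our specific platform features", it repeats the expectation of an average above 3. Freeform responses have a qualitative use: "The freeform survey feedback and discussions with sleep clinicians after the usability study will inform and design modifications".

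The same section treats completion time comparatively: "we expect to see average trial completion times significantly less for the DreamPort-Eclipse compared to the traditional mask". The sentence that introduces the ANOVA refers to average time and to technical issues: "number of technical issues will be computed and an analysis of variance (ANOVA) completed on the data set".

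**The concern.** A one-sample threshold cannot compare two options. The survey is introduced as covering both interfaces, in a study whose objective is comparative, but the only numerical use of its scores is to check one average against 3. If the plan is followed as written, the survey result says nothing about DreamPort-Eclipse relative to the mask, although every subject has worn both and is a natural control for himself or herself.

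There is also a practical side. Because the SUS sentence names no interface, three sites could administer it differently: once for DreamPort-Eclipse, once for the session as a whole, or once per interface. Section 6.3 has no follow-up, so a mask rating not collected on the day could not be obtained at a later planned visit.

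**Working it through.** **Step 1. What 8.2 plans for each measure.**

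| Measure | Contrast with the mask | Absolute benchmark |
|---|---|---|
| Setup time | Stated direction; named in the ANOVA sentence | DreamPort-Eclipse average under 5 minutes |
| Technical issues | Named in the ANOVA sentence | DreamPort-Eclipse, no more than 1 per subject |
| Additional instructions | Listed as a dependent variable; not named in the ANOVA sentence | None |
| SUS | None | Average above 3, interface not named |
| Custom survey | None | Average above 3, on the sponsor's platform |

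The list of dependent variables is worded as open-ended, but survey scores are not on it and nothing else supplies a survey contrast. DreamPort-Eclipse is the likely subject of the SUS sentence, because the sentences just before it concern that device. This is not stated.

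**Step 2. The plan's own figure.** The threshold of 3 and the sample size of 30 come without an alpha, power, effect size or SD, so there is no derivation to reproduce. On a 1 to 5 scale, 3 is the midpoint: (3 − 1)/(5 − 1) = 0.50. A true mean of exactly 3 would exceed the threshold in 50% of studies whatever the SD.

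**Step 3. What the threshold can tell apart.** Assume a true DreamPort-Eclipse mean of 3.5; this and all SDs below are assumptions. The chance that the average of n = 30 exceeds 3 is Φ((3.5 − 3) × √30 / SD), with √30 = 5.477:

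- SD 0.5: Φ(5.48), above 0.999
- SD 1.0: Φ(2.74) = 0.997
- SD 1.5: Φ(1.83) = 0.966

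The mask mean does not enter the formula. True mask means of 3.0, 3.5 and 4.0, which are differences of +0.5, 0 and −0.5 points, all give the same survey conclusion. This follows from the form of the criterion; the figures only illustrate it.

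**Step 4. What a paired estimate would give.** With both ratings from all 30 subjects, the 95% CI half-width for the mean difference is t(0.975, 29) × SD of differences / √30 = 2.045 × SD / 5.477 = 0.373 × SD:

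- SD of differences 0.5: 0.19 points
- SD of differences 1.0: 0.37 points
- SD of differences 1.5: 0.56 points

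A true difference of 0.5 points would be estimated usefully at the first two values and imprecisely at the third.

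**The case against.** The strongest reply is that the survey was never meant to carry the comparison. Section 8.1 says "The purpose of this study is to get feedback on the usability of the device prior to clinical trials", the freeform responses feed design changes, and no decision in the documents depends on a survey contrast. Absolute benchmarks for the new device are also the pattern of 8.2: the 5-minute and one-error expectations concern DreamPort-Eclipse alone. All of this stands and limits the weight of the point. It does not remove the mismatch between a survey introduced as covering both options and an analysis that uses no mask score.

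A second reply is that the ANOVA on the data set might take in the survey. The sentence names time and technical issues only. If survey scores were meant, 8.2 should say so.

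Third, the documents do not show how the SUS is administered. A reader might infer that it is completed once, for DreamPort-Eclipse only, and that the mask goes unrated. The text does not support this: the description of the survey is compatible with ratings of both interfaces, and the survey forms mentioned in sections 10.3 and 12.1 are not reproduced. What is absent is a planned comparison, not necessarily the data. The extra-item cost of the fix is conditional for the same reason.

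Finally, the figures in steps 3 and 4 rest on assumed means and SDs. They show neither a measured loss now nor a guaranteed gain.

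**Conclusion.** The point holds as a modest one. Section 8.2 gives survey scores an absolute expectation only, leaves the rated interface unnamed for the SUS, and plans no survey comparison with the mask, in a study whose objective and survey description are both comparative. Within the survey, a mean above 3 for DreamPort-Eclipse leaves open whether subjects found it better, worse or no different from the mask. This conclusion needs no assumed SD. Only the precision of a paired estimate does.

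Three stronger readings are tempting and are not supported. A reader might infer that the study as a whole cannot address its comparative objective, but setup time and technical issues are compared between interfaces. A reader might infer that a primary endpoint is left without a comparison, but section 4.1 mentions the survey separately from the listed primary endpoints. A reader might infer that the device passes on a midpoint threshold, but >3 is worded as an expectation and is not made a success rule.

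**What to change.** In section 8.2:

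1. State that each subject completes the SUS once for each interface at the end of the protocol, if the existing forms do not already do this. Randomise the order of the two forms or match it to device order.
2. State how the SUS score is computed from its items, and use the same score for both interfaces.
3. Report the mean for each interface and the paired DreamPort-Eclipse minus mask difference with a 95% CI (t, 29 df if all 30 complete both forms). Label it a supportive, non-primary estimate.
4. Tie the >3 expectation explicitly to DreamPort-Eclipse.

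If the sponsor wants formative feedback only, 8.2 should at least say that the survey is descriptive and which interface it rates. That removes the ambiguity but leaves the survey silent on the comparison.

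The cost is a few sentences and at most 10 extra items per subject (8 Usable plus 2 Learnable), with no added subjects or visits. The downsides are some extra burden after six trials and an imprecise contrast if the SD of differences is large. The result should therefore be read as an estimate with its interval and not as a test.

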## **9. MECHANICAL FAILURES, MALFUNCTIONS, AND DEFECTS**

During the usability study, our Bleep, LLC support team will problem solve any issues that arise with the study and provide support to ensure success of the study.

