### **6.2 *Index Procedure Data***

#### **6.2.1 *Index Procedure Details***

Index procedure details will be collected on all enrolled subjects. The Index procedure is defined as the SNAP CPAP usability protocol in accordance with the instructions for use (IFU). Such details related to this protocol may include, but are not limited to the following:

- Date of Usability Test
- Product Name, Catalogue Number, Lot Number
- Configuration Details
- Indication
- Accessory details
- All adverse events, device malfunction, and complications related to device or procedure

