### **13.5 Conflict of Interest Policy**

The independence of this study from any actual or perceived influence is critical. Therefore, any actual conflict of interest of persons who have a role in the design, conduct, analysis, publication, or any aspect of this study will be disclosed and managed. Furthermore, persons who have a perceived conflict of interest will be required to have such conflicts managed in a way that is appropriate to their participation in the study. The study leadership has established policies and procedures for all study group members to disclose all conflicts of interest and will establish a mechanism for the management of all reported dualities of interest.

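### Could sponsor support during testing, or set-ups that are never finished, distort the DreamPort-Eclipse set-up time enough to require a rule in the plan?

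*Combined protocol and SAP*

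**What the plan says.** Section 4.1 states: "The primary endpoints for this study will include time to complete each setup". It adds the number of technical issues and the "number of times subjects needed additional instructions". Section 3 sets the number of attempts: "Participants will be requested to put on each of the different CPAP interface options a total of three times", with device order randomized.

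In Section 8.2, "The average time to complete each trial and number of technical issues will be computed" and submitted to an ANOVA with subject ID and device as the independent variables. The section states an expectation of "overall an average time per subject of less than 5 minutes to setup the DreamPort-Eclipse", and a further expectation that the DreamPort-Eclipse will be significantly quicker than the mask.

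Section 9, on mechanical failures, malfunctions and defects, is a single sentence: during the study "our Bleep, LLC support team will problem solve any issues that arise with the study and provide support to ensure success of the study". Section 6.2.1 lists details that may be collected, among them "All adverse events, device malfunction, and complications related to device or procedure". Section 13.5 says: "The independence of this study from any actual or perceived influence is critical".

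The text available for review gives no start or stop point for the clock, no maximum time, no treatment of an attempt that is never completed, and no statement on whether sponsor staff may help while the clock runs.

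**The concern.** Two gaps seem to reinforce each other. Read at its widest, Section 9 lets the sponsor's own team step into a timed attempt with the sponsor's own device. A set-up that would have failed, or run long, then becomes a completed and perhaps shorter time. An attempt that is given up has no completion time, so a plain average leaves it out. If either happened more often with the DreamPort-Eclipse, its mean would look too good, both against 5 minutes and against the mask. The independence language in Section 13.5 makes sponsor involvement in a measured outcome look worse still. At stake is the credibility of the reported set-up time.

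**Working it through.** **What the documents supply.** There are 30 subjects and 3 attempts per device, so 30 × 3 = 90 timed attempts per device and 180 in all, which agrees with the six attempts per subject in Section 3. No SD, alpha, effect size or rate of non-completion is given, so there is no planned figure to reproduce. Everything below is illustration on assumed inputs.

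**1. How many unfinished attempts would matter?** Let *m* be the mean of completed attempts, *c* an assumed score for an unfinished attempt, and *f* the unfinished share. The mean over all attempts is (1 − *f*)*m* + *fc*, which reaches 5 when *f* = (5 − *m*)/(*c* − *m*).

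| *m* (min) | *c* (min) | *f* | Attempts of 90 |
|---|---|---|---|
| 4.5 | 10 | 0.5/5.5 = 0.0909 | 9 |
| 4.5 | 15 | 0.5/10.5 = 0.0476 | 5 |
| 4.0 | 10 | 1/6 = 0.1667 | 15 |
| 4.0 | 15 | 1/11 = 0.0909 | 9 |

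So 5 to 15 unfinished attempts of 90 (5.6% to 16.7%) would be needed. Losses on that scale would show in a simple count of attempts.

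**2. What if slow attempts vanish?** Times are taken as lognormal with *s*² = ln(1 + CV²) and *mu* = ln(mean) − *s*²/2, with correlation 0.5 on the log scale between a subject's attempts. Attempts longer than *L* are deleted; the rest are averaged within subject and then across subjects (1,000,000 simulated subjects).

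| True mean | *L* | CV 0.3 | CV 0.5 | CV 0.75 | CV 1.0 |
|---|---|---|---|---|---|
| 5.5 | 10 | 5.44 | 5.11 | 4.56 | 4.09 |
| 5.5 | 15 | 5.50 | 5.42 | 5.10 | 4.71 |
| 6.0 | 10 | 5.89 | 5.44 | 4.82 | 4.30 |
| 6.0 | 15 | 6.00 | 5.87 | 5.47 | 5.01 |
| 4.5 | 10 | 4.49 | 4.34 | 3.98 | 3.62 |

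For true means of 5.5 and 6.0, 3 + 2 = 5 of 16 cases fall below 5, all at CV 0.75 or 1.0. With correlation between 0.3 and 0.7 the same three cases at 5.5 fall below 5. The 5.01 entry is borderline, moving between 4.94 and 5.07. With a true mean of 4.5 the conclusion cannot change. The mechanism itself is not in the protocol: with no maximum time, a slow attempt ends when it is finished. Loss needs abandonment, which need not follow a time threshold.

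**3. How far does help move the mean?** Shift = share helped × minutes. From 5% × 1 min to 20% × 3 min this is 0.05 to 0.6 min, downward if help saves time and upward if the clock runs during troubleshooting.

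**4. What happens to the mask comparison?** The simulation used 30 subjects, 3 attempts on each of 2 devices, equal true means of 5.5 min, and a paired t-test on subject means at two-sided 5%, so 2.5% in one direction (20,000 studies per case).

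| Help pattern | False finding | CV 0.3 | CV 0.5 | CV 0.75 | CV 1.0 |
|---|---|---|---|---|---|
| Eclipse only, 5%, saves 1 min | Eclipse faster | 4.7% | 3.4% | 3.0% | 2.6% |
| Eclipse only, 10%, saves 2 min | Eclipse faster | 17.6% | 9.2% | 6.1% | 4.6% |
| Eclipse only, 20%, saves 3 min | Eclipse faster | 77% | 41% | 21% | 13% |
| Eclipse only, 10%, adds 2 min | Mask faster | 17.5% | 9.6% | 6.0% | 5.0% |

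Equal help on both devices gives 2.0–2.6% in favour of Eclipse, which is nominal. Inflation needs help confined to, or concentrated on, one device, and its direction depends on the clock. Dropped attempts were not modelled in this comparison; a rule that drops them would apply to both devices.

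**5. What does the text already catch?** The count of additional instructions in Section 4.1 is not restricted by who gives them, so sponsor help that instructs a subject naturally falls within it. Technical issues are a second primary count. Uneven help should therefore appear beside the time result, although neither count adjusts the time.

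**The case for a change.** The strongest contrary case is this. Section 9 is wide in its wording, whatever its heading. The DreamPort-Eclipse is new, while subjects already know CPAP, so difficulty, and with it help or abandonment, could plausibly be greater on that device. The counts do not repair a mean: nothing ties them to the recorded time, the sentence in Section 8.2 on what will be computed leaves out the instruction count, and Section 6.2.1 only says malfunctions may be recorded. A significant difference from the mask is expected, Section 11.6 foresees publication, and clock or completion data not captured on the day may be lost for good. A few sentences would be cheap.

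Part of this stands. The documents are silent on unfinished and assisted attempts, and one-sided help could matter, as the 77% extreme case shows. But it does not show that any stated rule gives a wrong result. Device-specific help is an inference that the documents neither state nor exclude. Section 9 most naturally describes technical and logistical support, and Section 13.5 is about disclosing and managing conflicts of interest, not assistance with set-up. Nor would writing something down settle the matter by itself: censoring, worst-rank scoring and a common maximum are different choices, the first two do not yield the simple mean that the 5-minute expectation refers to, and the documents support no particular maximum.

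**Conclusion.** No change to the plan is called for. The observation is correct as far as it goes: the treatment of unfinished and assisted attempts is unwritten. It is a missing detail, not an error. An analyst facing an abandoned attempt would ordinarily say that the mean covers completed attempts, state how many were not completed on each device, and read it beside the counts of instructions and technical issues.

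The size and direction of any effect are unknown. On the assumed inputs, help shifts the mean by 0.05–0.6 min either way. Equal help leaves the mask comparison at its nominal error. A falsely met 5-minute figure needs a true mean at or above 5; in the cases examined it also needed a CV of at least 0.75 and a cut-off that the protocol does not impose. The consequences are modest too: Section 8.1 describes a study meant to gather feedback before clinical trials, the 5-minute value is an expectation and not a success criterion, and the free-form comments, the survey question on stumbling blocks and the clinician discussions give other views of set-up difficulty.

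This conclusion rests on reading Section 9 as technical support and on help and abandonment not being concentrated on one device. If the counts showed that they were, the time comparison should be interpreted with that in view.
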